8.4 Expected Serious Adverse Events

- Emergent CABG.
- Stroke/TIA.
- Coronary perforation and cardiac tamponade.
- Peri-procedural MI related to acute vessel closure (troponin > 300 ng/L).
- Allergic reactions to the dye or medications used during the procedure.
- Major vascular complications as acute thrombosis, distal embolization, dissection, major bleeding (>2 gm% drop in hemoglobin, requiring blood transfusion, retroperitoneal bleeding or resulting in shock).pseudo-aneurysm, or arterio-venous fistula.
- Infection
- Cardiac arrest requiring resuscitation involving ventricular defibrillation/DC shock

8.5 Unexpected and fatal Serious Adverse Events

- Emergency endotracheal intubation.
- Pulmonary aspiration.
- All other serious adverse events that are not listed under " expected SAEs".
- Events that results into death.

8.6 Period for recording Serious Adverse Events

Data on serious adverse events will be collected from the time of procedure for the 1 month follow-up period.

9 Data Handling and Record Keeping

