Prolonged unnecessary fasting can often leave patients dissatisfied and add to the discomfort and anxiety of waiting for a procedure. Patients may also choose to miss their usual medications on the morning of the procedure due to restrictions advised with oral intake, increasing the risk of complications such as poorly controlled hypertension and the associated peri-procedural complications.

There is also evidence that patients often choose to fast longer than advised by healthcare professionals. The reasons for this include: misunderstanding by the patient that a longer period of fasting may be more protective, apprehension and loss of appetite before an invasive procedure, or practical problems with timing of the procedure.

It is very important to address this fasting issue as many patients undergo prolonged periods of fasting prior to a procedure and whilst this is not usually a problem for young fit patients, many of the patients do not fall into this category. Many are elderly with multiple co morbidities and thus run the risk of hypoglycaemia and lethargy.

A further consideration has to be that of patient flow through the cardiac unit. If patients have to be NBM for a certain period prior to cardiac catheterisation then it reduces the ability to fill lists at short notice if patients need to be cancelled. If we can demonstrate that this period of NBM is not necessary then we open the door to maximizing the catheter lab as a resource thus reducing length of stay. This improves patient experience along with the associated financial benefits.

Finally, and probably most importantly we feel that the overall patient experience will be improved if patients are allowed to eat up to the point of procedure decreasing the number of hungry, disgruntled patients who complain to nurses.

In essence, there is little evidence available about the benefits of pre-procedural fasting and prospective randomized trials are lacking with no clear guidelines recommendations that advocate the benefit of fasting prior to cardiac catheterization. Therefore, we aim to investigate the safety of this approach by this study.

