3.2 Study procedure

All patients to be admitted electively for coronary angiography or angioplasty will be given the opportunity to participate. An invitation letter together with patient information leaflet outlining the study will be sent along with the pre-procedure appointment letter to give the patient time to read and think about the study. Once at pre-procedure assessment clinic, the study will be explained further including potential risks and intended outcome and patients concerns will be addressed. Patient will be given the opportunity either to take part in the study or abstain and follow the standard procedure. If the patient agrees then they will sign the consent form and then be randomised in a 1:1 ratio to either the fasting or non-fasting group and be allocated a patient identification number. This will be done at the pre-procedure assessment clinic.

1- Fasting group (current practice): Clear fluids up to the time of the procedure and no food for at least 2 hours before the procedure.

2-Non Fasting Group: Clear fluids and food up to the time of the procedure.

The pre procedure preparation will then be documented in the notes. Intention to treat analysis will be used to avoid the effects of crossover and dropout providing unbiased comparisons among the treatment groups.

The case report form (CRF) will be appended inside the front cover of the notes to be completed on the day of procedure by the operating physician and the remainder completed by the research team. Finally once the patient is ready for discharge they will be asked to complete an anonymous questionnaire relating to their experience and satisfaction.

A database will be composed on an encrypted flash drive and backed up on the catheter lab computer. Only the patient identification number will be included in this but will still be password protected.

All patients will be contacted by phone on day 30 or the nearest working day thereafter to ensure no chest infections.

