4.3 Randomisation Process

Randomisation will take place in pre-procedure assessment clinic in a 1:1 ratio using sealed enveloped method. This information (whether fasting or not) will be relayed to the patient at the time of pre-procedure assessment and also stored on a spreadsheet with study number the only identifying factor. This will be password protected with individuals directly involved having access to this. This data will also be backed up on a password protected computer in the catheter laboratory.

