8.1 Recording of Adverse Events

All adverse events occurring during the study period will be recorded. The clinical course of each event will be followed until resolution, stabilisation, or until it has been determined that the study treatment or participation is not the cause. Serious adverse events that are still ongoing at the end of the study period will be followed up to determine the final outcome. The cardiac anaesthetic team has been made aware of the study in case a non-fasting patient need to be taken for emergency surgery.

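### Section 8.6 opens SAE collection at the procedure, so the pre-procedure period in which the arms differ lies outside the only defined SAE window

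*Combined protocol and SAP*

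**What the plan says.** Section 8.6 sets the SAE period: "Data on serious adverse events will be collected from the time of procedure for the 1 month follow-up period". No other section gives SAE collection a start.

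Two neighbouring sections are broader but undated. Section 8.1 says "All adverse events occurring during the study period will be recorded", and nowhere defines when that period begins or ends. Section 8.3 requires every SAE to be entered on the case report form (CRF) and likewise names no starting point.

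On timing of the intervention, section 4.3 says "Randomisation will take place in pre-procedure assessment clinic in a 1:1 ratio using sealed enveloped method", and adds that the patient learns the allocation at that visit. Section 3.2 describes the fasting arm as "Clear fluids up to the time of the procedure and no food for at least 2 hours before the procedure" and the non-fasting arm as "Clear fluids and food up to the time of the procedure".

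On possible harm before the procedure, section 2.1 says of patients who fast for prolonged periods: "Many are elderly with multiple co morbidities and thus run the risk of hypoglycaemia and lethargy". It also notes that patients often fast for longer than they were told to.

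**The concern.** The contrast under test takes place before the procedure. A window that opens at the procedure covers the after-effects of fasting or eating, but not the time when the patient is actually doing one or the other. If site staff follow section 8.6 as written, a serious event at home or on the ward before transfer has no clear place in the SAE data.

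Cancellation makes this sharper. A pre-procedure event serious enough to stop the procedure also removes the moment from which section 8.6 counts. Yet sections 4.1, 4.5 and 7.4 keep every randomised patient in the intention-to-treat analysis.

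At stake is how complete the safety record is. Section 2.1 closes by giving the safety of not fasting as the reason for the trial, and section 2.2 hopes that the result will inform national and international guidelines.

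**Working it through.** The plan states no figure on this point, so the check is a comparison of sections, followed by an illustration on assumed rates.

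**1. Order of events**
- Consent, randomisation and disclosure of allocation: pre-procedure assessment clinic (sections 3.2, 4.3, 4.4).
- Arms differ: from the start of fasting or free eating until the procedure (section 3.2).
- SAE window opens: at the procedure (section 8.6).
- SAE window closes: one month later (section 8.6).

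The second step lies wholly before the third. The exposure period is therefore outside the window in both arms.

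**2. Do other collection rules reach back?**
- Section 8.1: possibly, but only if its undefined study period starts before the procedure.
- Section 8.3: it covers all SAEs, with no start. It asks for the start date of each event, but a date alone cannot place a same-day event before or after the procedure.
- Section 7: the primary endpoint is recorded during or straight after the procedure and again within 8 hours. This does not reach back.
- Section 3.2: the operating physician fills in the CRF on the procedure day and the research team does the rest. No inquiry about the preceding hours is described.
- Section 3.4: hypoglycaemia and hypotension are secondary endpoints with no stated measurement time. They may pick up some pre-procedure events, but not SAEs in general.

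**3. The end of the window**

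Section 8.6 counts one month from the procedure. Section 3.5 puts the last contact 30 days after the last patient's enrolment. If enrolment means the clinic visit and the wait to the procedure is *W* days, that contact falls 30 − *W* days after the procedure. *W* is not given. Assuming *W* = 7 or 14, it falls at day 23 or day 16, short of the section 8.6 period.

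**4. Illustration of size (assumed rates)**

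Input: 200 patients per arm (section 7.1). The pre-procedure SAE rate *p* per arm is assumed, because the documents give none. Expected events outside the window = 200 × *p*. Chance of at least one = 1 − (1 − *p*)^200.

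| Assumed *p* | Expected events per arm | Chance of at least one |
|---|---|---|
| 0.1% | 0.2 | 18% |
| 0.5% | 1 | 63% |
| 1% | 2 | 87% |
| 1.5% | 3 | 95% |

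The table shows only that the answer depends entirely on *p*. It is not an estimate of *p*, and the true rate may be at or below the lowest row.

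**The case against.** The other side has several fair arguments.

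**Capture elsewhere.** A reader might infer that pre-procedure SAEs will simply go uncounted. The documents do not support that. Sections 8.1 and 8.3 can be read to include the wait, and hypoglycaemia, the harm that section 2.1 names, is an endpoint in its own right and not tied to section 8.6. This stands. What remains is that the one specific rule on the SAE period points the other way, and staff are not told which rule governs.

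**No comparison to bias.** A reader might infer a biased safety comparison. Sections 7 and 7.2 plan to compare the composite, satisfaction, hypoglycaemia, hypotension and 30-day chest infection. Section 8 treats SAEs as individual reports to the Chief Investigator, the sponsor and the ethics committee. No between-arm SAE test is planned, so none is shown to be biased. This stands.

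**No usable rate.** It is tempting to size the gap from the 1-2% in section 11. That figure is for nausea and vomiting, which section 8.2 classes as non-serious, and the composite has its own recording rule in section 7. It says nothing about missed SAEs.

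**Few serious events are likely.** Sections 2 and 2.1 place aspiration risk mainly in general anaesthesia and deep sedation, which would fall at or after the start of the procedure. The hypoglycaemia remark concerns prolonged fasting, whereas the fasting arm requires at least 2 hours without food. This limits the likely number. It does not remove the risk, since section 2.1 itself expects some patients to fast for longer.

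**Cancellation is a silent text.** Section 3.2 has all patients telephoned at day 30, which could bring an event to light. But the call is meant to check for chest infection, and the day from which it counts is not stated.

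**Conclusion.** The point holds in this form: the only defined SAE window excludes the period of randomised exposure, it gives no start for a patient whose procedure is cancelled, and it is not reconciled with sections 8.1, 8.3 and 3.5. Serious events before the procedure may therefore be recorded for some patients and not for others.

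The size is unknown and may be small. No figure in the plan changes, and neither the primary endpoint nor any planned test is affected through section 8.6. The conclusion assumes that section 8.6, as the specific rule, is at least as likely to be followed as the general wording of section 8.1. If site staff read section 8.1 as starting at randomisation, little would be lost in practice, but nothing in the text secures that reading.

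The change is worth making because safety is the trial's stated purpose and the correction is cheap.

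**What to change.** - Reword section 8.6 so that SAEs are collected in both arms from randomisation, or at the latest from the start of pre-procedure preparation, to 30 days after the procedure.
- Give patients whose procedure is cancelled an equivalent end date, for example 30 days after the planned procedure date, so that everyone in the intention-to-treat set has a defined window.
- Add a CRF item recording whether each SAE began before or after the start of the procedure, so that the two periods can be reported separately by arm.
- Define the study period in section 8.1 as the same interval, and refer to it in section 8.3.
- Reconcile section 3.5 and the day-30 call in section 3.2 with this end date, stating the day from which each counts.

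The cost is a wording change, the extra CRF item and a question on admission about events since the clinic visit. The CRF is not among the documents, so the work on the form cannot be checked. The downside is that some unrelated events during the wait will be recorded, more so if collection starts at randomisation, because the arms need not differ for most of that interval. The before/after item lets these be described separately.

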9.1 Confidentiality

Information about study subjects will be kept confidential and managed according to the requirements of the Data Protection Act and The Research Governance Framework for Health and Social Care.

- Subjects will be identified by Study number alone.
- All health professionals involved in the study and patient care will have access to this information if required.
- All patient data will be password protected in the computer in the cath lab
- If a patient needs to be identified for a clinical or safety reason, CI will be consulted.

The Chief Investigator (CI) is the custodian of the data.

9.2 Case Report Forms

The study case report form (CRF) is the primary data collection instrument.

- All data requested on the CRF/DCF will be recorded.
- All missing data will be explained. If a space on the CRF/DCF is left blank because the procedure was not done or the question was not asked, “N/D” will be written.
- If the item is not applicable to the individual case, “N/A” will be written.
- All entries should be printed legibly in black ink.
- To correct any data entry error, a single straight line will be drawn through the incorrect entry and enter the correct data above it. All such changes will be initialled and dated.

9.3 Records Retention

All records will be archived for 5 years in line with the Trust R&D Policy.

10 Study Monitoring, Auditing, and Inspecting

The investigator will permit study-related monitoring, audits and inspections by the Ethics Committee, the Sponsor and the Research Governance Manager.

Participation as an investigator in this study implies adherence to the principles and responsibilities of the Research Governance Framework, ICH/GCP and Directive 2000/20/EC

11 Ethical Considerations

The patient will receive a detailed description of the study in the patient information sheet send together with pre-procedure assessment letter by mail (around 1 week before the pre-procedure assessment clinic date) to give him/her time to think about the study. Then, at the pre-procedure assessment clinic, they will have the opportunity to ask questions with one of the research team and to answer any queries. Any patient will have the right to abstain from taking part into the study or to withdraw after taking part without affecting the standard of care they are receiving.

The Chief Investigator will ensure that the risk of the study does not outweigh the benefit at any point during the study time, and if so, the study will be prematurely terminated.

The benefit /risk of taking part into the study will be adequately explained to the patients. There will be no direct benefit to the patient from taking part in this study. However, the information gained from the study will help improve the quality of service offered to the patients, increase their satisfaction, may aid in changing the current practice and avoiding unnecessary delay to the patients. The potential risk will be made clear which is the occurrence of nausea and vomiting at an expected rate of 1-2% and no expected emergency endotracheal intubation or aspiration pneumonia cases.

Once patient is enrolled in the study, all his personal information will be anonymized with the only identifier the study number. All patient data will be password protected on the computer in the cath lab. All health professionals involved in the study and patient care will have access to this

information if required. Only the CI will have access to identify the patient personal data for the purpose of safety.

To ensure un-biased result, an adequate randomization process with intention to treat analysis will be undertaken. Analysis will be done by the Sub-Investigator who is blinded to group allocation.

